14.14 Protocol Deviations

Any departure from procedures and requirements outlined in the protocol will be classified as either a major or minor protocol deviation. The difference between a major and minor protocol deviation has to do with the seriousness of the event and the corrective action required. A minor protocol deviation is considered an action (or inaction) that by itself is not likely to affect the scientific soundness of the investigation or seriously affect the safety, rights, or welfare of a study participant. Major protocol deviations are departures that may compromise the participant safety, participant rights, inclusion/exclusion criteria or the integrity of study data and could be cause for corrective actions if not rectified or prevented from re-occurrence. Sites will be responsible for developing corrective action plans for both major and minor deviations as appropriate. Those corrective action plans may be reviewed/approved by the Lead Node and the CCC with overall approval by the site's IRB. All protocol deviations will be monitored at each site for (1) significance, (2) frequency, and (3) impact on the study objectives, to ensure that site performance does not compromise the integrity of the study.

All protocol deviations will be recorded in the electronic data capture AdvantageEDC system via the Protocol Deviation eCRF. The CCC, DSC and the Lead Investigator must be contacted immediately if an unqualified or ineligible participant is enrolled into the study.

Additionally, each site is responsible for reviewing their local IRB's definition of a protocol deviation or violation and understanding which events need to be reported. Sites must recognize that the CTN and IRB definition of a reportable event may differ and act accordingly in following all reporting requirements for both entities.

14.15 Safety Monitoring

14.15.1 Data and Safety Monitoring Board (DSMB)

The existing CTN-0051 DSMB will review the protocol and ICF prior to study initiation and will serve as the DSMB for this ancillary study. As this is an observational study and there is no treatment or other intervention, ongoing DSMB activities will be limited to updates on study progress (regulatory status, enrollment, protocol deviations and protocol-defined reportable safety events) at its regular meetings and notification of any issues of concern identified by the Lead Investigator or the Sponsor (NIDA).

14.15.2 Adverse Events (AEs)

For purposes of this study only overdoses, whether hospitalized or not, and all deaths will be collected. At weeks 1, 4 and 8, research staff will ask about any overdoses that have occurred since the last study contact. Additionally, any deaths from any cause will be reported on the AE form. No other AEs or SAEs will be captured in the course of this observational study. Reporting definitions and procedures are outlined in the Manual of Operations.

Each of the study sites has established practices for managing medical and psychiatric emergencies, and the study staff will continue to utilize these procedures. Treatment providers at each site will be responsible for monitoring participants for possible clinical deterioration or other problems, and for implementing appropriate courses of action.

14.15.3 Medical Monitor

The CCC Safety Monitor/Medical Monitor is responsible for overseeing safety and for evaluating all protocol-defined reportable safety events. The safety team will review/monitor protocol-defined reportable safety event information entered on the Adverse Event (AD1) eCRF on a weekly basis. No additional follow-up forms will be completed nor reviewed in the AdvantageEDC data system. Reporting definitions and procedures are further outlined in the Manual of Operations and research staff at each participating study site will be appropriately trained on safety event reporting for this protocol using only the AD1 eCRF in the AdvantageEDC data system.

The CCC Safety Monitor/Medical Monitor will report events to the Sponsor and regulatory authorities. Reports will be generated and presented for Data and Safety Monitoring Board (DSMB) meetings.

15.0 DATA MANAGEMENT

15.1 Design and Development

This protocol will utilize a centralized Data and Statistics Center (DSC). The DSC will be responsible for development of the electronic case report forms (eCRFs), development and validation of the clinical study database, ensuring data integrity, and training site and participating node staff on applicable data management procedures. AdvantageEDCSM, a web-based distributed data entry system, will be implemented. This system will be developed to ensure that guidelines and regulations surrounding the use of computerized systems used in clinical trials are upheld. The remainder of this section provides an overview of the data management plan associated with this protocol.

15.2 Site Responsibilities

The data management responsibilities of each individual site will be specified by the DSC and outlined in the AdvantageEDCSM User's Guide.

15.3 Data Center Responsibilities

The DSC will 1) develop a data management plan and will conduct data management activities in accordance with that plan, 2) provide final guided source documents and eCRFs for the collection of all data required by the study, 3) develop data dictionaries for each eCRF that will comprehensively define each data element, 4) conduct ongoing data monitoring activities on study data from all participating sites, and 5) rigorously monitor final study data cleaning.

15.4 Data Collection

The data collection process consists of direct data entry at the study sites into AdvantageEDCSM. In the event that AdvantageEDCSM is not available, the DSC will provide the sites with a final set of guided source documents and completion instructions. Data entry into AdvantageEDCSM should be completed according to the instructions provided. The investigator is responsible for maintaining accurate, complete and up-to-date records, and for ensuring the completion of the eCRFs for each research participant.

15.5 Data Acquisition and Entry

Completed forms and electronic data will be entered into the AdvantageEDCSM system in accordance with the AdvantageEDCSM User's Guide. Only authorized individuals shall have access to eCRFs.

15.6 Data Editing

Completed data will be entered into AdvantageEDCSM. If incomplete or inaccurate data are found, a query will be generated to the sites for a response. Sites will resolve data inconsistencies and errors and enter all corrections and changes into AdvantageEDCSM.

15.7 Data Transfer/Lock

Data will be transmitted by the DSC to the NIDA central data repository as requested by NIDA. The DSC will conduct final data quality assurance checks and "lock" the study database from further modification. The final analysis dataset will be returned to NIDA, as requested, for storage and archive.

15.8 Data Training

The study staff will be the same as the staff in CTN-0051. The training plan for CTP staff includes provisions for training on assessments, eCRF completion guidelines, and data management procedures.

15.9 Data Quality Assurance

To address the issue of data entry quality, the DSC will follow a standard data monitoring plan. An acceptable quality level prior to study lock or closeout will be established as a part of the data management plan. Data quality summaries will be made available during the course of the protocol.

15.10 Study Timeline

Study preparation will include obtaining IRB approval, applying for a Certificate of Confidentiality, receiving DSMB approval, developing the data collection system, developing the manual of operations, conducting all staff training, and endorsing sites. Recruitment is expected to take approximately 5-6 months, with follow-up continuing for approximately two months post completion of the recruitment phase. Two months will be allowed for data lock after the end of the follow-up period. Data lock is projected to occur concurrently with data lock for the parent protocol.

16.0 PUBLICATIONS AND OTHER RIGHTS

Per NIH Policy, the results of the proposed study are to be made available to the research community and the public at large. The planning, preparation, and submission of publications will follow the policies of the Publications Committee of the CTN.

19.0 APPENDIX A: DATA AND SAFETY MONITORING PLAN

1.0 BRIEF STUDY OVERVIEW

CTN-0051-A2 will collect a minimal data set on post-discharge to community TAU clinical outcomes for a similar group of participants leaving detox or short-term residential programs from the same sites as CTN-0051.

2.0 DATA AND SAFETY MONITORING BOARD (DSMB)

The existing CTN-0051 DSMB will review the protocol and ICF prior to study initiation and will serve as the DSMB for this ancillary study. As this is an observational study and there is no treatment or other intervention, ongoing DSMB activities will be limited to updates on study progress (regulatory status, enrollment, protocol deviations and protocol-defined reportable safety events) at its regular meetings and notification of any issues of concern identified by the Lead Investigator or the Sponsor (NIDA).

3.0 DATA MANAGEMENT PROCEDURES

This protocol will utilize a centralized Data and Statistics Center (DSC). A web-based distributed data entry model will be implemented. This electronic data capture system (AdvantageEDCSM) will be developed to ensure that guidelines and regulations surrounding the use of computerized systems in clinical trials are upheld.

The investigator at the site is responsible for maintaining accurate, complete and up-to-date research records. In addition, the Site Principal Investigator is responsible for ensuring the timely completion of eCRFs for each research participant.

4.0 DATA LOCK AND TRANSFER

At the conclusion of data collection for the study, the DSC will perform final data cleaning activities and will “lock” the study database from further modification. The final analysis dataset will be transferred to the Lead Investigator or designee. De-identified versions of these datasets will also be provided to the NIDA CCTN-designated parties for posting on Datashare, as well as storage and archiving.

Reference: <http://grants.nih.gov/grants/guide/notice-files/not98-084.html>

## LIST OF ABBREVIATIONS

Abbreviation	Definition
AE	Adverse event
CCC	Clinical Coordinating Center
CoC	Certificate of Confidentiality
DSC	Data and Statistics Center
DSMB	Data and Safety Monitoring Board
DHHS	Department of Health and Human Services
EDC	Electronic data capture
ERC	Ethics Review Committee
FWA	Federalwide Assurance
GCP	Good Clinical Practice
HIPAA	Health Insurance Portability and Accountability Act
ICF	Informed Consent Form
IRB	Institutional Review Board
LN	Lead Node
MAT	Medication-assisted treatment
MDMA	Methylenedioxymethamphetamine (Ecstasy)
NIDA	National Institute on Drug Abuse
NIH	National Institutes of Health
ODD	Opioid use disorder
PI	Principal Investigator
SAE	Serious adverse event
TAU	Treatment-as-usual
TLFB	Timeline Follow-Back
UDS	Urine drug screen

## **1.0 INTRODUCTION**

### **1.1 Study Objective**

CTN-0051-A2 (also referred to as “ancillary study”) is an observational study intended to describe opioid use amongst opioid use disorder patients following their discharge into the community from inpatient detoxification and/or short-term residential treatment programs affiliated with CTN-0051 (referred to as “parent study”).

### **1.2 Study Design**

This is an observational study of participants with opioid use disorder leaving 5 of the detoxification and/or short-term residential units from which participants for CTN-0051 are recruited, but who are discharged to TAU in the community. Similar drug use measures but not identical are collected in this study as in CTN-0051. The goal is to estimate (1) days to first use and days to regular use, (2) number of days of use during the first four and eight weeks post-discharge to the community, and (3) number of positive, negative and missing UDSs at weeks 1, 4 and 8 post-discharge to the community.

### **1.3 Treatment/Intervention**

There is no treatment or intervention in this study.

### **1.4 Database Sources**

Completed forms and electronic data will be entered into the data management system in accordance with the CRF Completion Guidelines established by the DSC. Only authorized individuals shall have access to electronic CRFs.

### **1.5 Randomization**

There is no randomization in this study.

### **1.6 Study Population**

Approximately three hundred sixty (360) participants will be enrolled. Participants will be patients that were admitted to detoxification or short-term residential programs associated with CTN-0051 for opioid use disorder and that were discharged to the community.

#### **1.6.1 Participant Inclusion Criteria**

1. 18 years of age and older;
2. Meet DSM-5 criteria for opioid-use disorder (heroin or prescription opioids);
3. Have used opioids other than as specifically prescribed within thirty days prior to consent;
4. Seeking treatment for opioid dependence;
5. Able to provide written informed consent; and
6. Able to speak English sufficiently to understand the study procedures.

#### **1.6.2 Participant Exclusion Criteria**

1. Serious medical, psychiatric or substance use disorder that, in the opinion of the Site Principal Investigator (PI), would make participation hazardous to the participant, compromise study findings or prevent the participant from completing the study;
2. Suicidal or homicidal ideation that requires immediate attention;

3. Maintenance on methadone at doses of 30mg or greater at the time of signing consent;
4. Presence of pain of sufficient severity as to require ongoing pain management with opioids;
5. Currently in jail, prison or any inpatient overnight facility as required by court of law or have a pending legal action which may prevent an individual from completing the study;
6. If female, currently pregnant or breastfeeding or planning on conception; or
7. Prior participation in parent study CTN-0051.

### **1.6.3 Participant Recruitment**

Participants will be recruited from the same detoxification and/or short-term residential programs participating in CTN-0051. Candidates admitted for opioid use disorder will be approached by research staff and provided information about the study.

## **2.0 OUTCOMES AND SUBGROUPS OF INTEREST**

The outcomes are (1) days to first opioid use and days to regular use, (2) number of days of use during the first four and eight weeks post-discharge to the community, and (3) number of positive, negative, and missing UDSs at weeks 1, 4, and 8. The number of participants abstinent for four weeks and those participants who were not will also be calculated.

### **2.1 Timeline Follow-back (TLFB)**

The Timeline Follow-back procedure was used to elicit the participant's self-reported use of substances at baseline and throughout study participation. At screening, this form was used to assess substance use for the 30-day period prior to admission to the inpatient treatment program. At Week 1, the TLFB assessed the period from discharge to the community up to the date preceding the Week 1 visit (the time in detox and/or short-term residential was not captured on this assessment). At weeks 4 and 8, the TLFB was used to assess each day since the previous TLFB assessment.

### **2.2 Urine Drug Screens**

Urine was collected for a urine drug screen at each in-person study visit. All urine specimens were collected using FDA-approved one-step temperature-controlled urine drug test cups following all of the manufacturer's recommended procedures. The UDS tested for the presence of the following drugs: opioids, oxycodone, barbiturates, benzodiazepines, cocaine, amphetamine, methamphetamine, marijuana, methadone, and ecstasy (MDMA). Two additional single strip tests were performed: one for buprenorphine (BUP10) and a more sensitive test for opiates (OPI300). In the event urine specimen tampering was suspected, either based on the observation or the adulterant tests, study staff should have requested a second urine sample and may have observed the urine collection process according to clinic standard operating procedures.

### **2.3 Treatment Plans**

To evaluate the outcomes, two main sub-groups from the observational cohort are (1) participants who receive any medication-assisted treatment (MAT) and (2) participants who do not receive medication-assisted treatment. Assessment of the participant's intention for treatment after discharge to community (i.e., leaving the detox and/or short-term residential unit) was assessed at the Day 0 visit (Community Discharge Plan). On the Medical Management (MM) Community Treatment form, at weeks 1, 4 and 8, participants were asked what treatment(s) he/she was engaged in, with the options being

- (1) MAT with buprenorphine maintenance
- (2) MAT with injectable naltrexone
- (3) MAT with oral naltrexone
- (4) MAT with methadone maintenance
- (5) MAT with inpatient detox
- (6) Psychosocial
- (7) Referral to other community-based treatment
- (8) Declined further treatment.

A participant will be categorized as having received any medication-assisted treatment post-discharge if at any visit (Weeks 1, 4, and 8), the treatment plan engaged in includes medication-assisted treatment.

Program type and high severity vs. low severity at baseline will also define groups to be separately analyzed. The program type subgroups will be defined based on the length of stay in the detox and/or residential facility. The date of admission to the detox unit is found on the Detoxification Utilization Summary form and the corresponding dates of discharge for both the detox unit and residential facility are found on the enrollment form. If the subject was discharged to the community from the residential facility, the total time in detox and the residential facility will be calculated. The difference between admission and discharge dates will be tabulated and categorized based on the following groupings: (1)  $\leq 7$  days, (2) 8-20 days and (3)  $\geq 21$  days.

High severity and low severity opioid use level at baseline will be defined as computed for the main CTN-0051 study stratification factor (i.e.  $< 6$  bags vs.  $\geq 6$  bags). To compute the opioid severity level, if the primary opioid of use in the last 7 days was not heroin or the route of administration is not IV-injection then that participant is defined as a low severity user. For IV heroin users where the quantity is not provided in bags but in dollars, bags are estimated as the dollar amount/10 rounded to the nearest integer.

All outcomes listed in Sections 5.1-5.4 will be calculated separately for each of these subgroups of the observational cohort, as well as in the overall study sample.

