10.10 Retention Plan

Participants will be tracked for follow-up using the same methods and rigor employed in the CTN-0051 parent study. Assessments may be collected by telephone as a last resort.

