13.5 Missing Data and Dropouts

The number of missing as well as the number of positive and negative UDSs will be tabulated separately when calculating the UDS outcome at weeks 1, 4 and 8. Analyses of self-reported use will impute intermittent missing days as use, but will not impute missing days due to dropout or loss-to-follow-up.

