### **5.1 Days to First Opioid Use**

The days to first opioid use will be tabulated based on the data collected on the TLFB where only illicit use is recorded. The days to first opioid use will begin being assessed on Day 0 where Day 0 is defined as the day of discharge into the community. An opioid use day is defined as use of any of the opioids reported on the TLFB including Buprenorphine, Opioid analgesics, Methadone, or Heroin. The first instance of use by self-report is defined as the first opioid use day.

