### **5.5 Analysis Methods**

For modeling the days to first opioid use and days to regular opioid use outcomes measures, a Cox regression model will be used after an assessment of the proportional hazards assumption. Should the key proportional hazards assumption be violated for a particular outcome and covariate, alternative models will be considered. The second set of outcomes relate to the number of days of opioid use. It is anticipated that the number of days of use will be non-normal, however we elect to analyze the data via a *t*-test which is fairly robust to misspecification of the underlying outcome distribution. Quantile regression may be used if modeling with multiple covariates is appropriate. For UDS-based outcomes, the dependent variable is binary (i.e., indicator of use or indicator of missingness) so univariate comparisons will be made using Pearson's  $\chi^2$  and any multivariate modeling will be implemented using logistic regression.

The second set of outcomes relate to the number of days of opioid use. It is anticipated that the number of days of use will be non-normal, however we elect to analyze the data via a *t*-test which is fairly robust to misspecification of the underlying outcome distribution. Quantile regression may be used if modeling with multiple covariates is appropriate. For UDS-based outcomes, the dependent variable is binary (i.e., indicator of use or indicator of missingness) so univariate comparisons will be made using Pearson's  $\chi^2$  and any multivariate modeling will be implemented using logistic regression.

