## **6.0 MISSING DATA**

The number of missing as well as the number of positive and negative UDSs will be tabulated separately when calculating the UDS outcome at baseline, and weeks 1, 4 and 8. Analyses of self-reported use time to event outcomes (e.g. time to first use) will impute intermittent missing days as use, but will not impute missing days due to drop-out or loss-to-follow-up. When tallying the days of opioid use, all missing self-reported days will be imputed as positive. The number of days imputed for each subject will also be summarized.

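### The MAT / No-MAT label is read from Weeks 1 to 8 while outcomes run from Day 0, so later relapse and attendance can set the subgroup; the size, and possibly the sign, of the days-of-use artefact depends on the missing-day rule

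*SAP*

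**What the plan says.** - **Label.** Under SAP 2.3 a participant is "categorized as having received any medication-assisted treatment post-discharge if at any visit (Weeks 1, 4, and 8" the treatment engaged in includes MAT. Option 5 on the form lists inpatient detox as a kind of MAT. Intended treatment is recorded at Day 0 but does not set the label.
- **Clock.** SAP 5.1: "The days to first opioid use will begin being assessed on Day 0", the day of discharge to the community. SAP 5.2 does the same for regular use.
- **Split.** The end of SAP 2.3: "All outcomes listed in Sections 5.1-5.4 will be calculated separately for each of these subgroups of the observational cohort". The shells for Tables 8, 11, 14 and 17 have only MAT, No-MAT and Total columns, and Figures 2 and 5 draw one curve per treatment type.
- **Model.** SAP 5.5 names a Cox model, a t-test and a chi-square test. It does not say how MAT enters the Cox model. For UDS, "the dependent variable is binary (i.e., indicator of use or indicator of missingness".
- **Missing days.** Protocol 13.5, on self-reported use generally: "will impute intermittent missing days as use, but will not impute missing days due to dropout or loss-to-follow-up". SAP 6.0 agrees for time to event, but then says: "When tallying the days of opioid use, all missing self-reported days will be imputed as positive".
- **Mitigation.** Protocol 10.10: "Assessments may be collected by telephone as a last resort". SAP 2.1: "At weeks 4 and 8, the TLFB was used to assess each day since the previous TLFB assessment". Table 17 reports imputed days by MAT column.

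**The concern.** The label is a post-discharge variable, completed up to eight weeks after the clock starts. Three routes to a spurious MAT difference follow.

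1. **Relapse can set the label.** A participant who relapses in Week 2, is readmitted and reports inpatient detox at Week 4 can be labelled MAT, and the relapse is then charged to MAT. Conversely, someone who must stay abstinent long enough to start MAT brings event-free time into the MAT group.
2. **Attendance can set the label.** A participant with no Community Treatment form cannot report MAT. If such participants go to No-MAT, that column collects the dropouts, and SAP 6.0 scores their missing days as use.
3. **UDS missingness becomes partly circular.** Table 14 splits missing screens by a label that attendance helped to set.

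At stake is how the MAT columns are read. Protocol 13.3 names the MAT subgroups in its primary-objective sentence, although Protocol 5.1 names no subgroup and 13.3 also places them under secondary exploratory outcomes.

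**Working it through.** **The plan's own scale.** No figure in the documents measures this bias, so I first checked the hazard-ratio scale in Table 1 of SAP 3.2.4. Treating the 0.5 as the SD of a 50:50 binary covariate, power = Φ(√(D × 0.25) × ln HR − 1.96).
- N=360, 60% events: D=216, HR 1.47, power 80.8% (stated 82%).
- N=360, 70% events: D=252, HR 1.45, power 83.9% (stated 84%).

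The plan therefore treats 1.45 to 1.47 as a detectable effect.

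**Time to first use, no MAT effect.** Inputs: 60-70% use by Week 8 (SAP 3.2.4). Assumed: exponential times, 30% on MAT at discharge, 10-30% later entry. A Cox model on ever-MAT in 400,000 simulated participants gives:
- entry unrelated to use: HR 1.00;
- entry only before first use: 0.69-0.88;
- only users enter later: 1.17-1.68.

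The ranges move with how entry is modelled. This shows that bias is possible, not which way it goes.

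**Days of use, no MAT effect.** Inputs: visits at days 7, 28 and 56. Assumed: monotone loss d per visit, unrelated to use or MAT; 30% on MAT at discharge, then 10% of those not yet on MAT before each of Weeks 4 and 8; true mean 14 days, so p = 14/56 = 0.25.

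Let k be the number of visits attended.
- Probability q: d, (1−d)d, (1−d)²d, (1−d)³ for k = 0 to 3.
- Missing days: 56, 49, 28, 0.
- Probability of the MAT label: 0, 0.30, 0.37, 0.433.

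At d = 0.10, q = 0.100, 0.090, 0.081, 0.729.
- MAT mean missing days: (0.027×49 + 0.030×28)/0.3726 = 5.8.
- No-MAT: (0.100×56 + 0.063×49 + 0.051×28)/0.6274 = 16.1.
- Difference: −10.3.
- SAP 6.0 scores each missing day 1 instead of p: −10.3 × 0.75 = −7.7.
- Protocol 13.5, *if* an unimputed day counts as zero use: −10.3 × (−0.25) = +2.6.
- With never-seen participants (k=0) removed from No-MAT, its mean is 4.516/0.5274 = 8.6 and the difference is −2.8, giving −2.1 under SAP 6.0 and +0.7 under that reading of Protocol 13.5.

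| MAT minus No-MAT, days | 5% | 10% | 20% |
|---|---|---|---|
| SAP 6.0, no-form in No-MAT | −4.4 | −7.7 | −12.1 |
| SAP 6.0, unknown column | −1.1 | −2.1 | −3.3 |
| Protocol 13.5, unimputed days = 0, never-seen score 0 | +1.5 | +2.6 | +4.0 |
| Same, never-seen treated as missing | +0.4 | +0.7 | +1.1 |
| Percent of observed days | 0 | 0 | 0 |

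These losses mean 14, 27 and 49% lost by Week 8. If 25, 50 or 75% of missed visits are done by telephone, −7.7 becomes −4.2, −1.9 or −0.6.

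**Week 8 UDS missing, same scenario,** MAT against No-MAT: 8% v 19%, 15% v 34%, 30% v 57.5%.

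**Check of the remedy.** MAT as a time-dependent covariate, and a Week 1 landmark, both return null HRs of 0.99-1.01 under the users-only and before-use-only rules.

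**The case against.** The best defence is that this is an exploratory split in a descriptive study. Protocol 13.4 and SAP 5.5.1 disclaim formal testing, SAP 3.3 promises caution and confidence intervals, telephone contact and look-back TLFBs shrink the problem, and Table 17 discloses imputed days by column. All of that stands and limits the severity. It does not remove the point: SAP 3.3 and 5.5 still set a 5% level and name tests, and a descriptive column can mislead without a p-value.

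The sizes rest on assumed loss, uptake and telephone rates; the documents give none. Placing no-form participants in No-MAT is an inference from two-column shells, and it supplies about 73% of the SAP 6.0 figure ((7.7 − 2.1)/7.7). The text's silence on these participants is itself a gap.

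A reader might infer more than the documents support:
- **That Protocol 13.5 reverses the sign.** It says only that dropout days are not imputed, not that they count as zero use or that a never-seen participant scores 0. The reversal needs the zero-use reading. On percent of observed days, a measure SAP 5.0 mentions, there is no artefact in this scenario. With no dropout the two rules agree. If uptake is one third as high after first use and 20-40% are lost, both rules favour MAT (−0.1 to −3.0 days under Protocol 13.5 with unimputed days as zero, −10.7 to −14.9 under SAP 6.0).
- **That time to use is biased in a known direction.** It may go either way or be nil.
- **That a test of missingness by MAT is planned.** SAP 5.5 lists missingness as a compared outcome but does not say by MAT.

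**Conclusion.** The point holds and should be fixed. On the text alone, a label built from Weeks 1, 4 and 8 groups outcomes counted from Day 0 with nothing to protect against reverse influence, and option 5 lets readmission after relapse count as MAT. With no true effect, the first-use HR can lie anywhere from about 0.7 to 1.7, including 1.00, depending on assumed uptake.

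Under SAP 6.0, dropout alone can make No-MAT look worse by roughly 4 to 12 days in the illustrated scenarios, or 1 to 3 days once no-form participants are shown separately, and less with telephone contact. Protocol 13.5 gives a different answer, whose sign depends on how unimputed days are scored.

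Confidence is high that the rule can create a spurious difference; the sizes are illustrations. A reader might also conclude that the study's main estimates are compromised by the label. They are not: the overall treatment-as-usual figures do not use it. The missing-day discrepancy affects the overall days-of-use tally in its own right.

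**What to change.** 1. **SAP 5.5.** Enter MAT in the Cox models as a time-dependent covariate, starting from no MAT reported, updated at each visit and never backdated. Present the Day-0 plan as a separate split labelled intended treatment.
2. **Tables 8, 11, 14, 17 and Figures 2, 5.** Show participants with no Community Treatment form as unknown.
3. **Ever-MAT split.** Keep it as labelled description. Do not test it, and do not test UDS missingness by it. Add a Week 1 landmark as a sensitivity analysis (status among those seen at Week 1, outcomes from Week 1).
4. **Missing days.** Reconcile Protocol 13.5 with SAP 6.0 on dropout days, state how unimputed days are scored, and report percent of observed days used beside the imputed count.

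**Cost.** SAP wording and modest programming; the variables are already collected. The time-dependent term treats MAT begun at discharge as unexposed until Week 1, which would dilute an early effect. The landmark loses F(7)/F(56) = 18-20% of first-use events under constant hazard with 60-70% use by Week 8. The loss is 26% if 65% use by Week 4 (the proportion Protocol 4.1 gives for the Geneva cohort) and up to 53% if use is also front-loaded (Weibull shape 0.5). It leaves differential retention: if MAT participants are lost at half the rate, −1.2, −2.4 and −4.5 days remain under SAP 6.0. The Day-0 plan describes intended, not received, treatment, and confounding remains under any grouping.
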